Further protocol-based treat to target period (w32 until 104)

After w32, patients will continue on the therapy assigned to their treatment arm. Patients not maintaining or not reaching the target of LDA beyond the accelerated access time window (w8-w32), will go to the next step in the protocol-based adaptation scheme further detailed in the protocol. In accordance with the latest EULAR recommendations patients should be further treated to a target of at least LDA but this can be adapted to remission at the investigators discretion.

After completing this 2-year randomized controlled trial, all patients will be asked to give consent for roll over into a 3-year observational follow-up trial.

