SUSAR	Suspected Unexpected Serious AR
SAE	Serious Adverse Event
SC	Sub Cutaneous
SIV	Site Initiation Visit
SJC	Swollen Joint Count
SSZ	Sulfasalazine
STMG	Study Team Management Group
TARDIS	Tool for Administrative Reimbursement Drug Information Sharing
TB	Tuberculosis
T2T	Treat to Target
TJC	Tender Joint Count
TNF	Tumor Necrosis Factor
TSC	Trial Steering Committee
VAS	Visual Analog Scale
w	week
WPAI	Work Productivity and Activity Impairment

Trial flow chart

- All adaptations are triggered by LDA (DAS28CRP>3,2) except for w32, there remission (DAS28CRP \geq 2,6) will be applied
- *MTX=Methotrexate
- Etanercept in the Early Etanercept adaptation will be given for 24 weeks
- \diamond Randomization point (1:1), every patient will be randomized once

	Screen	BL	W4	W8	(W12)	W16	(W20)	W24	(W28)	W32	(W36)	W40	(W44)	(W48)	W52	(W56)	(W60)	W64	(W68)	W78	(W82)	W91	(W95)	W104
Informed consent	x																							
Inclusion/Exclusion criteria	x																							
Demographic data	x																							
Medical history	x																							
Assessment of comorbidities	x																							
Clinical/neuromatological examination	x	x	x	x	x	x	x	x	x	x	x	x	x	x	x	x	x	x	x	x	x	x	x	
RF and ACPA status	x																							
ESR/CRP	x	x	x	x	x	x	x	x	x	x	x	x	x	x	x	x	x	x	x	x	x	x	x	
TB screening*	x																							
X-Ray hands/feet	x																							
DAS28 CRP/ESR	x	x	x	x	x	x	x	x	x	x	x	x	x	x	x	x	x	x	x	x	x	x	x	
PRO's**:	x	x	x	x	x	x	x	x	x	x	x	x	x	x	x	x	x	x	x	x	x	x	x	
Employment status	x	x	x	x	x	x	x	x	x	x	x	x	x	x	x	x	x	x	x	x	x	x	x	
Randomization/procedure																								
Relevant Concomitant medication (SAR's and SAE's of interest)	x	x	x	x	x	x	x	x	x	x	x	x	x	x	x	x	x	x	x	x	x	x	x	

(X) Optional

* According to local guidelines, to be repeated in case of starting bDMARD beyond 6 months after initial testing

** PRO's: HAQ, VAS scales done in routine; RAID, ECD5, WPAL, PASS added to evaluate disease specific activity, health economics and patient acceptance, total duration of PRO collection about 10 min.

Flowchart	Screen	BL	W4	W8	W12	W16	W20	W24	W28	W32	W40	W44	W48	W52	W56	W60	W64
Randomized at W8	x	x	x	x	x	x	x	x	x	x	x	x	x	x	x	x	x
Randomized at W16	x	x	x	x	x	x	x	x	x	x	x	x	x	x	x	x	x
Randomized at W24	x	x	x	x	x	x	x	x	x	x	x	x	x	x	x	x	x
Randomized at W32	x	x	x	x	x	x	x	x	x	x	x	x	x	x	x	x	x
Not randomized	x	x	x	x	x	x	x	x	x	x	x	x	x	x	x	x	x

General mandatory visit	R+28w
General optional visit	R+24w

Mandatory visits for randomized patients	R+16w
	R+8w

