In this pragmatic, prospective, multicenter, randomized, controlled trial of 2-year duration, 442 patients with early RA (≤ 1 year), previously untreated with DMARDs (disease modifying anti-rheumatic drugs), will be included. A subgroup of insufficient responders to the initial COBRA-Slim remission induction regimen will be randomly assigned, during a time window between w8 and w32, to 2 different treatment strategies.

Randomization will be balanced according to time-point of randomization, BL disease activity and RF/ACPA status using the minimization technique (see statistical plan). Patients who do not meet the criteria for randomization, during the so-called accelerated access period, will still follow the common adaptation strategy during the remaining part of the study.

Initial protocol-based treat to target period (BL until w32):

All participants will receive at BL a COBRA-Slim remission induction regimen, which includes:

- Methotrexate 15 mg PO weekly (starting from 10 mg weekly for 2 weeks)
- Step down scheme of GC: 30-20-12,5-10-7,5-5 mg prednisone PO daily, each for 7 days except for the lowest dose of 5 mg, this will be maintained until w28 and then tapered to 2.5 mg daily for two weeks before stopping completely.

In case at any evaluation moment from w4 until w32 (not included) patients do not reach low disease activity (LDA = DAS28CRP \leq 3.2), the MTX dose will be increased to 20 mg PO weekly.

If after this first adaptation patients still not achieve or maintain a sufficient response during the period from week 8 until 32 (the accelerated access period), they will be considered insufficient responders.

Insufficient responders are defined as:

Patients not reaching LDA (DAS28CRP \leq 3.2) at any evaluation moment from week 8 until 32 after the first adaptation (a previous MTX increase).

Patients not reaching remission (DAS28CRP $<$ 2.6) at the week 32 evaluation visit irrespective of a previous MTX increase.

These insufficient responders will be randomly assigned to one of two different treatment strategies:

Group 1: Standard COBRA-Slim Induction:

Addition of leflunomide 10mg PO daily as the next step in the protocol-based CareRA2020 treatment adaptation scheme.

If target of LDA is still not reached or maintained minimally 12 weeks after the initiation of Leflunomide, treatment has to be adapted according to the next step of the adaptation scheme.

Group 2: COBRA-Slim Bio-induction with accelerated access to anti TNF:

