Addition of etanercept 50mg Subcutaneous (SC) weekly for a period of 24 weeks in this accelerated access arm as the next treatment adaptation.

If target of LDA is still not reached or maintained minimally 12 weeks after the initiation of etanercept, treatment has to be adapted according to the next step of the CareRA2020 adaptation scheme.

Randomization will be balanced according to time-point of randomization, baseline (BL) disease activity and Anti-Citrullinated Protein Antibody (ACPA) and/or Rheumatoid Factor (RF) status to ensure comparability of the treatment groups with respect to these prognostic variables.

Patients who do not meet the criteria for randomization, during the so-called accelerated access period, will all follow the same CareRA2020 treatment adaptation scheme, further detailed in the protocol.

Further protocol-based treat to target period (w32 until w104):

After w32, patients will continue on the therapy assigned to their treatment. In case LDA is lost or still not reached during this protocol-based treat to target phase, treatment will be adapted

according to CareRA2020 adaptation schedule (table 1 page 28). A next adaptation is only allowed after the previous treatment adaptation has reached its full strength, so minimally after the time period specified for each adaptation step (table 2 page 28).

In accordance with the latest EULAR recommendations patients should be further treated to a target of at least LDA but this can be adapted to remission at the investigators discretion.

The minimal dose of MTX required according to protocol is 15 mg PO per week except in case of documented toxicity, then 7.5 mg PO or parenteral is allowed. In case MTX has to be discontinued, Leflunomide should be given at a dose of 20 mg PO daily or 10 mg PO in case of documented toxicity (see paragraph “Treatment toxicity during study”, page 30).

CareRA2020 adaptation schedule

As a first adaptation, from w4 onwards, MTX should be increased to 20mg weekly PO. The next adaptation steps are summarized in table 1.

One exception is the w32 visit, at which a MTX dose increase is not needed, and one should proceed to the second adaptation step.

After w32, adaptation of MTX or leflunomide is at the investigators discretion, but when LDA is not reached one should proceed to the next adaptation step.

Table 1: protocol defined adaptations

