Adaptations	Patients randomized to Standard COBRA-Slim Induction	Patients randomized to COBRA-Slim Bio-induction with accelerated access to Etanercept	Patients NOT randomized
2 nd	Add leflunomide 10mg/day PO	Add etanercept 50mg/week SC for 24 weeks*	Add leflunomide 10mg/day PO
3 rd	Replace leflunomide by etanercept (50mg/week SC*) (per reimbursement)	Add leflunomide 10mg/day PO and stop etanercept if it has not been already stopped	Replace leflunomide by etanercept (50mg/week SC*) (per reimbursement)
4 th	Treatment at the discretion of the rheumatologist	If previous response** to etanercept: Replace Leflunomide by etanercept (50mg/week SC) (per reimbursement)	If NO previous response** to etanercept: Treatment at the discretion of the rheumatologist
5 th	Treatment at the discretion of the rheumatologist	Treatment at the discretion of the rheumatologist	Treatment at the discretion of the rheumatologist

* check for latent TB if not already done within 6 months

** Previous response: If patient completed the 6 months course of etanercept and maintained LDA without toxicities during this period.

Adaptations are only allowed after the current treatment has reached its full strength, so minimally after the time period specified in table 2, or in case of toxicity.

Table 2: protocol defined time to next adaptation:

Medication	Time to be re-evaluated
Methotrexate dose increase	At least 4 to 8 weeks
Leflunomide initiation	At least 12 weeks
Etanercept or other bDMARD initiation	

General rules for treatment adaptations during the study from baseline until w104

If patients fail to achieve or maintain low disease activity (DAS28CRP \leq 3.2), protocol-based treatment adjustments will be made from 4 weeks of treatment onwards until w104.

The only exception to this rule is at w32, the end of the remission induction phase, where treatment response will not be targeted at LDA but at remission (DAS28CRP $<$ 2.6). If patients at w32 fail to reach remission, a treatment adaptation is required, unless a previous treatment adaptation has not yet reached its full strength (table 2).

In accordance with the latest EULAR recommendations patients should be further treated to a target of at least LDA but this can be adapted to remission at the investigators discretion after w32.

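### The protocol gives two different week-32 triggers for patients already randomised, so those in low disease activity but not remission are told both to continue and to change treatment

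*Combined protocol and SAP*

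**What the plan says.** Two sets of rules cover a randomised patient at the w32 visit.

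**LDA only.** In section 3, Initial protocol-based treat to target period, each arm has one trigger for the next step. For Group 1 it is "If target of LDA is still not reached or maintained minimally 12 weeks after the initiation of Leflunomide"; for Group 2, "If target of LDA is still not reached or maintained minimally 12 weeks after the initiation of etanercept". The Trial Summary (Treatment adjustments during study) sets the target at DAS28CRP ≤ 3.2 from week 4 to w104. It names no w32 exception and permits other adaptations only for toxicity or discomfort.

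**Remission at w32.** In section 3, General rules for treatment adaptations, w32 is the single exception to the LDA rule, "where treatment response will not be targeted at LDA but at remission". The operative sentence is "If patients at w32 fail to reach remission, a treatment adaptation is required, unless a previous treatment adaptation has not yet reached its full strength". The Trial flow chart agrees: "All adaptations are triggered by LDA (DAS28CRP>3,2) except for w32". Neither place limits the exception to patients not yet randomised.

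**What an adaptation means.** In Table 1 the Bio-induction arm's second step is "Add etanercept 50mg/week SC for 24 weeks" and its third is "Add leflunomide 10mg/day PO and stop etanercept if it has not been already stopped". The Standard arm's third step replaces leflunomide by etanercept, per reimbursement.

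**The concern.** A calendar-week rule and a time-since-randomisation rule meet at w32. They disagree for patients who are in LDA but not in remission and whose add-on has been running for at least 12 weeks. Sites cannot settle this by judgement. Section 3 lets the DAS28CRP result be overruled only for isolated foot involvement or a recent infection, and the option to aim for remission is given for the period after w32.

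Three things are at stake:

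- The primary objective concerns a 24-week etanercept course, and one reading shortens that course in patients who meet their arm's own target.
- Remission 28 weeks after randomisation (R+28w) is one of only two endpoints tested at the 5% level, and the same reading can put controls on etanercept before it.
- Section 10 defines the per-protocol set by whether the required adaptations were performed. While two rules stand, following one is a deviation from the other.

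**Working it through.** **1. The plan's own figure.** The main secondary endpoint assumes remission of 50% against 80%, two-sided alpha 0.05, 1:1 allocation, with 80 or 92 completers.

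Power = Φ{[0.30 − 1.96 × √(2 × 0.65 × 0.35 / n)] / √[(0.5 × 0.5 + 0.8 × 0.2) / n]}

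- n = 40 per arm: 81.6% (stated 82%)
- n = 46 per arm: 86.7% (stated 87%)

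The published figures reproduce. The point does not rest on an error in them.

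**2. Who is exposed under the general rule.** Inputs: randomisation at w8, w16, w24 or w32, with w12, w20 and w28 also allowed (section 6); full strength at 12 weeks for either add-on (arm paragraphs and Table 2); a 24-week course (Table 1); endpoint at R + 28.

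| Randomised (R) | Weeks on add-on at w32 (32 − R) | At least 12? | Weeks short of 24 | R+28w visit | Weeks from w32 to R+28w |
|---|---|---|---|---|---|
| w8 | 24 | yes | 0 | w36 | 4 |
| w12 | 20 | yes | 4 | w40 | 8 |
| w16 | 16 | yes | 8 | w44 | 12 |
| w20 | 12 | yes, just | 12 | w48 | 16 |
| w24 | 8 | no | exempt | w52 | exempt |
| w28 | 4 | no | exempt | w56 | exempt |
| w32 | 0 | no | exempt | w60 | exempt |

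Early loss of etanercept is therefore possible for w12, w16 and w20. A control switch before R+28w is possible for w8, w12, w16 and w20. These are nominal dates.

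**3. One patient under both rules.** Take a patient randomised at w16 with DAS28CRP 3.0 at w32.

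- Arm paragraphs: LDA is met, so treatment continues in either arm.
- General rules with Table 1: remission is missed and the add-on is at full strength. In the Bio-induction arm etanercept stops after 16 of 24 weeks and leflunomide is added. In the Standard arm leflunomide is replaced by etanercept, if reimbursed.
- Knock-on effect: the Bio-induction patient no longer meets Table 1's definition of previous response, which needs a completed course. The fourth step changes as a result.

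**4. How many.** The documents give neither the distribution of randomisation visits nor the share of patients at 2.6-3.2 at w32. Assume 104 randomised, spread evenly over the four dedicated visits, and a share of 10-25%.

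- Bio-induction, w16 only: 104 × 0.25 × 0.5 × 0.10 = 1.3; with 0.25, 3.25. About 1-3 patients.
- Standard, w8 and w16: 104 × 0.50 × 0.5 × 0.10 = 2.6; with 0.25, 6.5. About 3-7 patients, or 5-12.5% of 52.

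**5. Illustration of dilution, not an estimate.** Suppose 10% of controls had an 80% chance of remission instead of 50%. The control rate becomes 0.50 + 0.10 × 0.30 = 0.53. The formula in step 1, with n = 46 and 0.53 against 0.80, gives 79% instead of 87%.

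**The case against.** The best reply is that specific text governs general text. The arm paragraphs were written for randomised patients, and the adaptation schedule's own remark on w32 sends patients to the second step, which fits those not yet randomised. This reading is available. It is not stated, however, and the general rules present w32 as an exception to the very LDA rule that the arm paragraphs apply.

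The opposite certainty is also tempting. A reader might infer that the w32 trigger definitely covers randomised patients, because the full-strength exemption refers to Table 2, where leflunomide and etanercept appear. Table 2 also lists the methotrexate increase, so the exemption has a use for patients not yet randomised. The inference does not settle the matter.

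Other parts of the reply stand:

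- The Trial Summary's line "After w32, patients will continue on the therapy assigned to their treatment arm" concerns the period from w32 onwards and does not clearly govern the w32 visit itself.
- Patients not in LDA can move to the third step from 12 weeks after randomisation under either reading. Some crossover before R+28w is part of the strategies being compared, and the AUC is meant to reflect successive adaptations.
- The control switch depends on reimbursement.
- The primary analysis is by intention to treat; the per-protocol analysis is supplementary.
- Section 2 already plans to report treatment changes and use of biologicals at R+28w.

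**Conclusion.** The conflict is real and needs no assumption to show. For patients randomised from w8 to w20 with DAS28CRP 2.6-3.2 at w32, the protocol states two incompatible instructions and no order of precedence. Because the conflict decides who stops and who starts the study drug, and who counts as per protocol, it is more than a matter of wording. On the assumptions above it touches about 1-3 Bio-induction patients and 3-7 controls, over and above the planned switching of patients not in LDA. If etanercept is the more effective step, as the trial hypothesises, the direction is dilution of the R+28w contrast. The size cannot be derived from the documents. Severity: moderate.

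Some stronger conclusions are not supported:

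- A reader might infer that patients randomised at w8 also lose part of their course. They do not: 32 − 8 = 24 weeks. Being four weeks off etanercept at R+28w is what a 24-week course implies by design.
- A reader might pool everyone into one count, 104 × 0.5 × (0.10 to 0.25) = 5-13. That mixes early stopping with control crossover and includes w8 Bio-induction patients, whose course is not cut.
- A reader might infer demonstrated bias in either endpoint. The documents show only a possible direction.

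**What to change.** Reconcile the Trial Summary target, the Trial flow chart, the Group 1 and Group 2 paragraphs and the general rules with Tables 1 and 2. The result should be one statement of which trigger applies at w32 to patients already randomised. Which one is for the sponsor to decide. Define per-protocol membership by that statement, and list the patients already handled under the other reading.

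In the report, give by arm and randomisation visit:

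- the number whose etanercept stopped before 24 weeks while in LDA;
- the number of controls who switched at w32 while in LDA.

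These tables add disease-activity status and timing to the biological-use counts already planned.

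A remission contrast at R+24w would not serve as a remedy. That visit coincides with w32 only for patients randomised at w8; for w16 it falls at w40, eight weeks after a w32 switch.

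The cost is a protocol clarification, a short patient listing and two tables. No new visits or data are needed.

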 - HAQ response at 28 weeks after randomization and at w104
2. Radiographic progression: X-ray evolution at w52 and w104 compared to BL as reviewed and evaluated by the central team.
3. Side effects: (S)ARs from BL until w104
4. To evaluate the primary outcome using the DAS28ESR instead of the DAS28CRP.

Other secondary, exploratory outcome measures:

1. Clinical effectiveness:

A) In the randomized early insufficient responder population (w8-w32) with or without accelerated access to a six-month course of etanercept.

Effectiveness:

- AUC of DAS28CRP/DAS28ESR during 28 weeks after randomization
- Time to first remission during 28 weeks after randomization
- Sustained remission = remission for at least 24 weeks (BL-w104).
- Number of treatment changes, number of patients able to follow the protocol, number of patients using biologicals and/or GC at 28 weeks after randomization and at w104.
- Cumulative doses of GC and analgesic use at 28 weeks after randomization and at w104.

B) In the complete study population, including the randomized groups of insufficient responders, each completed with an early responder control population.

Effectiveness:

- Sustained remission = remission for at least 24 weeks (BL-w64, BL-w104, w64-w104).
- Number of treatment changes, number of patients able to follow the protocol, number of patients using biologicals and/or GC throughout the entire study

- Cumulative doses of GC and analgesic use throughout the entire study
- 2. Treatment response in terms of PROs:
 - Patient acceptable symptom state (PASS) and RA Impact of Disease (RAID) at 28 weeks after randomization and at w104
 - PASS at w64 and w104.
 - RAID at w 64, 104.
- 3. Cost-effectiveness:
 - WPAI / EQ5D questionnaire at 28 weeks after randomization and at w104
 - Per-protocol and out-of-protocol medication use as well as the number of outpatient visits and occasional hospitalization

[figure not shown]
Depending on the clinical results of the trial, a health economic analysis may be justified. This could be part of a health technology assessment project at KCE. Quality of life data as well as the national number of the participating patients are collected in this trial to facilitate a possible economic analysis.

3 Study design

Overall design

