In case of an epidemic like the COVID-19 outbreak, the health of patients and coworkers are the first priority. On the other hand, adequate follow-up of patients, with a chronic condition and in need of a chronic treatment, is essential. Interruption of treatment is contraindicated, not for conventional nor for biological or targeted synthetic DMARDs, except in case of active infection or other complications and preferably on the advice of the treating rheumatologist.

Data collected during telephone consultations will be transcribed by the sites at the correct visit page in the e-CRF, marking the box of the telephone visit next to the date field. This way data management can clearly discriminate between data collected by phone and during outpatient consultations.

BL data (w0)

The following information will be captured from routine clinical data (SoC) at Week 0 visit:

- Clinical/Rheumatologic examination
- Joint Count: TJC, SJC
- Weight
- ESR and CRP (in case screening blood samples were taken within 5 days, these values can be used).
- DAS28CRP/DAS28ESR (in case screening blood samples were taken within 5 days, these values can be used)
- VAS PhGA/GH/pain/fatigue
- HAQ
- Relevant concomitant medication
- Relevant side effects
- Changes in employment status

Apart from the above information following PROs will be collected from the patients specifically for the study:

- RAID
- EQ5D/WPAI

Trial assessments

(A schematic overview can be found at page 21)

At week 4, 12, 20, 28, 48, 56, 68, 82, 95 or unscheduled visit following data are captured as part of routine clinical data collection (SoC):

- Clinical/Rheumatologic examination
- Joint Count: TJC, SJC
- Weight
- ESR and CRP
- DAS28CRP/DAS28ESR
- VAS PhGA/GH/pain/fatigue
- Relevant concomitant medication
- Relevant side effects
- Changes in employment status

Randomization procedure is optional and is preferably done at the dedicated visits (w8, 16, 24 or 32). In case randomization is required in between these visits, when LDA is not reached, it is allowed at week 12, 20 and 28.

At week 8, 16, 24, 32, 40, 64, 78 and 91 following data are captured as part of routine clinical data collection (SoC):

- Clinical/Rheumatologic examination
- Changes in co-morbidities assessment (co-morbidity shortlist only at w32)
- Joint Count: TJC, SJC
- ESR and CRP
- DAS28CRP/DAS28ESR
- VAS PhGA/GH/pain/fatigue
- HAQ
- X-ray (Sharp/van der Heijde Score) only for w24 visit
- Relevant concomitant medication

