- Relevant side effects
- Changes in employment status

Apart from the above information following PROs and assessments will be collected specifically for the study at these time points:

- RAID
- EQ5D/WPAI
- PASS (only w64)
- Randomization procedure in case LDA is not reached between w8 and w32, and in case remission is not reached at w32. This randomization procedure will be done preferable at the dedicated time points w8, w16, w24 or w32 but when required is also allowed in between these visits. This can be done with an optional procedure at visit w12, 20 or 28.

At yearly and endpoint visits (week 36, 44, 52, 60 and 104) following data are captured as part of routine clinical data collection (SoC):

- Clinical/Rheumatologic examination
- Joint Count TJC, SJC
- Weight
- Changes in co-morbidities assessment (co-morbidity shortlist only at w52 and 104)
- RF and ACPA status only at w104
- ESR and CRP
- X-Ray hands/feet (Sharp/van der Heijde Score) on a yearly basis
- DAS28CRP/DAS28ESR
- VAS PhGA/GH/pain/fatigue
- HAQ
- Relevant concomitant medication
- Relevant side effects
- Changes in employment status

Apart from the above information following PROs and assessments will be collected specifically for the study at these time points:

- RAID
- EQ5D/WPAI
- PASS (only w52 and 104)

Withdrawal of patients

Any patient may withdraw from the study for any reason at any time. The investigator may withdraw any patient from the study if it is not in the patient's best interest to continue.

In this trial, all included patients will be followed according to the protocol for the complete study period unless they withdraw consent, are lost to follow up or die.

Protocol violations in relation to the therapeutic strategy will not be considered a reason to interrupt follow up within the CareRA2020 study.

In case the proposed treatment schedule cannot be followed due to serious safety concerns, the patient will be kept in the study for further follow up and treated at the discretion of the investigator, taking into account the interest of the patient and the feasibility of the treatment.

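### Section 6 lists no HAQ, RAID, EQ5D or WPAI at w48 and w56, the 28-week visits of patients randomised at w20 and w28; PASS has a wider gap

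*Combined protocol and SAP*

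**What the plan says.** **Outcomes (section 2, Outcome measures/endpoints).** Four lines are tied to the randomisation date. "HAQ response at 28 weeks after randomization and at w104" is among the other secondary outcomes. "Patient acceptable symptom state (PASS) and RA Impact of Disease (RAID) at 28 weeks after randomization and at w104" and "WPAI / EQ5D questionnaire at 28 weeks after randomization and at w104" are among the exploratory ones.

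**Randomisation visits (section 6, Trial assessments).** The preferred visits are w8, w16, w24 and w32, with an allowance for the visits between them: "In case randomization is required in between these visits, when LDA is not reached, it is allowed at week 12, 20 and 28". The allowance is repeated later in the same section: "This can be done with an optional procedure at visit w12, 20 or 28".

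**What is collected when (section 6, Trial assessments).** There are three visit groups, each with its own list.
- "At week 4, 12, 20, 28, 48, 56, 68, 82, 95 or unscheduled visit following data are captured": examination, joint counts, weight, ESR/CRP, DAS28, VAS scales, medication, side effects and employment. HAQ, RAID, EQ5D and WPAI are absent.
- "At week 8, 16, 24, 32, 40, 64, 78 and 91 following data are captured as part of routine clinical data collection": this list adds HAQ, RAID and EQ5D/WPAI, with PASS at w64 only.
- "At yearly and endpoint visits (week 36, 44, 52, 60 and 104) following data are captured as part of routine clinical data collection": this list also has HAQ, RAID and EQ5D/WPAI, with PASS at w52 and w104 only.

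**Which visits are compulsory (section 6, Visits).** The table of visits that become mandatory after randomisation has rows for w8, w16, w24, w32 and non-randomised patients, and none for w12, w20 or w28.

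**Windows (section 7, Time schedule).** Up to w64 the aim is one week either side of the target date; w8 has no window before it.

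**The concern.** The third visit group is labelled as containing endpoint visits, and w36, w44, w52 and w60 are exactly R+28w for the four preferred randomisation visits. The schedule appears to have been built around those four and not extended to the in-between visits that the same section permits.

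A patient randomised at w20 or w28 may therefore reach the 28-week time point with no scheduled functional, impact, quality-of-life or work-productivity questionnaire. A questionnaire that was not completed cannot be recovered later. The analyst would have to treat the value as missing or borrow one from another visit, and the plan gives no rule for the second course.

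**Working it through.** **Inputs.** Permitted randomisation visits and the three visit groups come from section 6, Trial assessments; the 28-week time point from section 2; the window from section 7, Time schedule. No plan figure has to be reproduced. The check is to add 28 to each permitted visit and look up the result.

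| Randomised at | R+28w | HAQ, RAID, EQ5D, WPAI listed? | PASS listed? |
|---|---|---|---|
| w8 | 8 + 28 = w36 | yes | no |
| w12 | 12 + 28 = w40 | yes | no |
| w16 | 16 + 28 = w44 | yes | no |
| w20 | 20 + 28 = w48 | **no** | no |
| w24 | 24 + 28 = w52 | yes | yes |
| w28 | 28 + 28 = w56 | **no** | no |
| w32 | 32 + 28 = w60 | yes | no |

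The results for w8, w16, w24 and w32 agree with the R+28w visits in Table 4 of section 10. Two of the seven permitted visits fail for the four questionnaires, and six of seven fail for PASS.

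**Nearest listed values.**
- Randomised at w20 (target w48, window w47 to w49): w44 = R+24w and w52 = R+32w.
- Randomised at w28 (target w56, window w55 to w57): w52 = R+24w and w60 = R+32w.

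Each is 4 weeks from target against a tolerance of 1 week.

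**Can these randomisation visits occur?** Yes. Table 2 in section 3 allows re-evaluation from 4 weeks after a methotrexate increase. An increase at w16 can thus lead to randomisation at 16 + 4 = w20, and one at w24 to randomisation at 24 + 4 = w28.

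**Are w48 and w56 compulsory for these patients?** Nothing says so. Both are marked optional in the schedule of procedures, and no mandatory-visit row covers randomisation at w20 or w28. For w12 the missing row matters less, because w40 is already among the mandatory visits named for the primary analysis in section 10.

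**Size.** The documents do not give the share randomised at w20 or w28. For scale only, each 5% of the planned 104 randomised patients is 104 × 0.05 = 5.2 patients, or 92 × 0.05 = 4.6 of the 92 expected to remain after 11% dropout. This is not an estimate. The preferred visits may absorb nearly all randomisations.

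**The case against.** **The schedule may already cover these visits.** The schedule of procedures has one PRO row, and its footnote names HAQ, VAS, RAID, EQ5D, WPAI and PASS. A mark at w48 and w56 could mean that all are collected. A reader might infer from the section 6 list that the questionnaires are definitely not collected and the outcomes cannot be measured; the documents do not establish that. Nor does the row settle the matter the other way. The VAS scales belong to the same row and are the only PROs that section 7 requires at every visit, so they alone could explain a mark. The text copy of the row also has 23 marks for 24 visit columns and cannot be aligned with confidence. What stands is an ambiguity between text and table that has to be resolved.

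**Bias between arms.** Etanercept in the accelerated arm is planned for 24 weeks, so a reader might infer that taking the nearest visit would score that arm while still on drug and distort the comparison. The documents contain no substitution rule. The nearest values lie equally early (R+24w) and late (R+32w), so no direction of error follows. Minimisation on timing should also spread these patients over both arms.

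**Importance.** Section 10, Secondary outcome analysis, treats every secondary outcome other than the main one as explorative, with no significance claim. The economic analysis is only a possibility. This objection stands and limits the weight of the point.

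**Conclusion.** The point holds as a mismatch between the outcome definitions and the data-collection schedule. On the section 6 lists, patients randomised at w20 or w28 have no scheduled HAQ, RAID, EQ5D or WPAI within the window of their 28-week time point. The nearest listed values are 4 weeks early or late, and no rule allows their use. PASS is affected more widely, being scheduled at R+28w only after randomisation at w24.

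The consequence is lost information on explorative outcomes in a group whose size is unknown. The questionnaire gap does not reach the primary outcome, the main secondary outcome or EULAR response, since DAS28 is listed at w48 and w56. That those two visits remain optional is a separate weakness, and it does bear on whether the 28-week DAS28 is obtained in these patients.

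The conclusion assumes that the written lists in section 6 govern. If the PRO row was meant to include all instruments at every marked visit, the defect becomes a contradiction between table and text, and the same clarification is needed.

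**What to change.** - In section 6, Trial assessments, add HAQ, RAID and EQ5D/WPAI at w48 for patients randomised at w20, and at w56 for patients randomised at w28.
- Add rows for w12, w20 and w28 to the mandatory-visit table, so that the R+28w visit (w40, w48, w56) is compulsory for them.
- Add PASS at every randomised patient's R+28w visit.
- Have the e-CRF patient schedule open these forms from the randomisation date. Section 6 says it already shows the visits that become mandatory after randomisation.
- Align the PRO row of the schedule with the lists, stating which instruments apply at which visit.

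The cost is a text edit, an e-CRF trigger, one visit made mandatory for a minority of patients, and about 10 minutes of questionnaires at that visit (the schedule footnote's figure for the full PRO set). For patients randomised at the other visits the only addition is PASS, where it is not already listed.
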